5.5 Study Evaluations

Table 5 shows the study measures and data collection schedule. We will send self-administered questionnaires to participants via mail with the option to complete and return by postage-paid mail. If the participant does not return the questionnaires by mail within two weeks, we may send a reminder letter or a study coordinator may attempt to administer them by telephone. To improve retention and the likelihood that participants will complete the follow-up evaluations, we will send a letter reminding them of their participation in the study at around the 4th, 8th, 16th, and 20th month after randomization.

5.5.1 Baseline Variables and Co-variates:

We will collect baseline variables and co-variates from CDW to the extent possible, and supplement with participant self-report surveys, MFP logs, and/or paper trackers.

5.5.2 Outcomes:

• Weight:

- For all participants, we will extract all outpatient-based weight measurements from CDW starting with 12 months prior index date through 27 months of follow up. For participants without a CDW weight:
 - We may include a reminder with the outcomes surveys to visit their primary care clinic to be weighed if a clinic visit is safe and feasible.
 - During times when a clinic visit is not feasible (i.e., currently, during SARS-CoV-2 pandemic), we will include a self-weight form with the outcomes surveys for those without a CDW weight to weigh themselves at home. The self-weight survey and instructions for self-weighing will be in lieu of a reminder to visit their clinic to avoid encouraging participants seeking medical care unnecessarily, given public health guidance to avoid healthcare settings for anything other than urgent care requiring in-person contact. All participants without a 24-month CDW outcome will be asked to self-weigh using a letter asking the participant to weigh themselves using the scales provided by DELITE at baseline. The mailing will include instructions about how to make the measurement (e.g., light indoor clothing, no shoes or other heavy items), a form to record the weight, and a postage-paid return envelope. If we do not receive a mailed response from participants within 2-weeks, a study coordinator may call the participant and ask them to weigh themselves and report the weight over the telephone.

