 - A participant's primary outcome weight will be the one measured closest to 12 months AND between nine and 15 months, in a primary care-based clinic, and extracted from CDW. We will consider other weights as secondary outcomes.
- To validate clinic weights, we asked some VA Puget Sound HCS/CBOC participants to visit the Seattle or American Lake campus for an in-person weight collected by study staff. We coordinated those visits with an existing clinic visit to have a clinic-based weight for comparison. If the scheduled visit is in a non-primary care clinic, we may ask the participant if we may accompany them to primary care for a weight check. If primary care does not enter the weight into CPRS, [name] may do so. We have completed this process as of early 2020 and won't add it again, given the pandemic.

- Generic health status: Assessed using the SF-12⁵⁵ at 12 months as a primary outcome and at 24 months as a secondary outcome. The SF-12 has been extensively tested and shown to be valid, reliable and responsive to change.
- Reach: We selected the most relevant measure for the present trial from the well-established RE-AIM framework⁷²: "reach," defined as the "number, proportion, and representativeness of individuals willing to participate in a given intervention." First, we will estimate the proportion of those eligible who agreed to participate, with total recruitment letters sent, and total eligibility screenings conducted as denominators.

Second, we will capture “representativeness” by comparing participants’ demographic characteristics to the VA patient population and to those who were eligible for the study.

- Physical activity: 7-item International Physical Activity Questionnaire (short IPAQ) which evaluates weekly walking, vigorous and moderate-intensity activity.⁷³
- Dietary quality/self-efficacy: Starting the Conversation⁷⁴ questionnaire with items pertaining to fat, fruit and vegetable intake, and sugar intake, as well as diet self-efficacy measures.⁷⁵
- Sleep-Related Disturbance and Impairment: 4-item sleep disturbance and 8-item sleep-related impairment scales from the NIH PROMIS measures.⁷⁶
- Blood pressure: diastolic and systolic values from 12 months prior index date to 27 months follow-up will be obtained from the CDW.
- Blood sugar levels: HbA1c levels from 12 months prior index date to 27 months follow-up will be obtained from CDW

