12-Month Outcome (Testing Method)	Significance Level	Power	Scenario Type	Mean Diff. (SD) Cohen's d	Sample Size (w/ 20% Attrition)	
					Per-Group	Total
Weight (ANOVA, with adjustment for baseline weight)	0.025	0.90	Mean Diff. = 7.7 SD = 50.0 Corr. b/w Baseline, 12-Mo. Measures = 0.97	7.7 (50.0) d = 0.154	78	156
			Conservative (25% Cohen's d reduction, Corr. = 0.95)	6.7 (57.7) d = 0.116	225	450
SF-12 PCS (t-test)	0.025	0.90	MCID = 5.00 SD = 8.88	5.00 (8.88) d = 0.563	100	200
			Conservative (25% Cohen's d reduction)	4.33 (10.25) d = 0.422	176	352

5.6.2 Retention:

As in other studies, we will carefully train and regularly review with staff best practices for retaining participants, including fully informed roles and responsibilities of staff and participants, and conveying an appreciation of participation and study identification. We will train staff to conduct effective informed consent to assure that participants fully understand the demands and nature of the study before they enroll. Coordinators will carefully review study requirements with participants, explain the concept of random assignment and what each treatment involves, and stress the importance of follow-up assessment even if they are not adhering to their assigned

treatment. We will use a database to systematically track participant activities, prompt the study team when action is required, and regularly produce quality control reports, all proven elements for participant retention.

5.6.3 Hypothesis Testing and Statistical Analyses:

We will use intention to treat (ITT) for all primary and secondary analyses. We will evaluate the dropout and missing data patterns for informative missingness⁸². To test for non-zero intervention effects on weight and SF-12 PCS, we will compare mean outcome between intervention and control groups at 12 month follow-up using the repeated-measures mixed-effects linear model:⁸³⁻⁸⁵

$$y_{ij} = \beta_0 + \beta_1(j) + \beta_2(\text{InterventionFollowUp}_{ij}) + \beta_3(\text{Age65Plus}_i) + \beta_4(\text{BMICat1}_i) + \beta_5(\text{BMICat2}_i) + \beta_6(\text{Urban}_i) + \alpha_i + e_{ij}$$

y_{ij} is the outcome (weight or SF-12 PCS) for patient i at baseline ($j = 0$) or 12-month follow-up ($j = 1$).

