We anticipate that any misclassification of outcome measurement will be non-differential with respect to randomization and effectively biasing our results toward the null. We will attempt to minimize misclassification by using approaches to decrease measurement error within the CDW data as well as by collecting patient-measured data when necessary. We will use data collected from primary care clinics preferentially. We will not collect weight data that was part of hospital admissions because of potential of changes in weight due to management. We will ask participants to use the scales provided only when not available in the CDW. If we find no evidence of informative missingness we will be able to rely on our use of well-specified mixed models to test effects of the intervention as these are known to lead to valid conclusions even when data are missing at random (MAR).^{87,93} If we detect informative missing data patterns, we will apply sensitivity analyses using pattern mixture models.⁸² Complete case analysis will only be performed as a sensitivity analysis, to provide useful inference if the data are mostly complete and the bias introduced by dropping the small proportion of incomplete cases is negligible.

5.6.6 Interim Analyses:

We plan no formal interim analysis of efficacy or futility. We will provide interim safety reports semi-annually to the Data Monitoring Committee (DMC).

5.7 *Withdrawal of Subjects*

We do not anticipate a need to withdraw a participant from the research entirely. If a participant becomes pregnant, we become aware of a serious physical or mental health issue, or the participant's primary care provider notifies us that the individual should not continue the intervention, the participant will cease participation in the intervention activities of the research; however we will continue to follow the individual through completion of the study via CDW and self-report.

If a participant chooses to withdraw him/herself from the research, we will confirm with the individual that we may continue to follow him/her in CDW. If the individual declines, we will respect his/her choice and not collect additional data from CDW; however we will use any data collected up to the date of withdrawal.

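### Pattern-mixture analysis is run only if informative missingness is detected, so departures from missing at random could go unexamined for both co-primary outcomes

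*Combined protocol and SAP*

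**What the plan says.** Section 5.6.3 announces a screen: "We will evaluate the dropout and missing data patterns for informative missingness". It gives no test, threshold or decision rule. Section 5.6.5 then branches on the result. On one branch, "If we find no evidence of informative missingness we will be able to rely on our use of well-specified mixed models", with MAR as the stated condition for validity. On the other, "If we detect informative missing data patterns, we will apply sensitivity analyses using pattern mixture models". The pattern-mixture model is not specified. The only other missing-data analysis is complete case: "Complete case analysis will only be performed as a sensitivity analysis", tied to data that are mostly complete.

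The primary model in Section 5.6.3 has two time points per participant: its response "is the outcome (weight or SF-12 PCS) for patient i at baseline" or at 12 months. It has a random intercept, stratum covariates, a common baseline mean and one treatment coefficient at follow-up.

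Both outcomes can be missing for reasons linked to how the participant is doing. Under Section 5.5.2 the primary weight "will be the one measured closest to 12 months AND between nine and 15 months, in a primary care-based clinic". SF-12 depends on a completed questionnaire. "If the participant does not return the questionnaires by mail within two weeks", the plan allows a reminder letter or a telephone attempt.

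**The concern.** MAR and its alternatives cannot be told apart from the observed data. Patterns by arm, baseline value or stratum can raise suspicion, but they cannot rule out that a participant is missing because of the 12-month value nobody saw. A screen is therefore the wrong gate for an analysis whose purpose is to ask what happens if MAR fails.

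Complete case does not fill the gap, because with a single follow-up it rests on essentially the same information and the same assumption as the primary model. If the screen is quiet, the report would contain two agreeing results, and that agreement would say nothing about MAR. What is at stake is mainly the stated size of benefit, and, if the true effect is smaller than planned, possibly the conclusion.

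**Working it through.** **Inputs.** Section 5.6.1 and Table 6: 500 enrolled (250 per arm); 20% attrition, so 200 observed and 50 missing per arm; two-sided alpha 0.025 (critical z 2.2414); power 90%. Weight: 7.7 lb, SD 50, r 0.97; conservative 6.7 lb, SD 57.7, r 0.95. PCS: 5.00, SD 8.88; conservative 4.33, SD 10.25. Section 2.3.1: E-LITE PCS difference 2.0; change SDs 4.7 and 6.5; baseline SD 7.5.

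**The plan's own figures.** n per arm = 2 × (2.2414 + 1.2816)² × SD² × (1 − r²) / difference², divided by 0.8. Weight: 62, then 78 (stated 78). Conservative weight: 180, then 225 (stated 225). PCS, with r = 0 and t-based: 80, then 100 (stated 100). Conservative PCS: 141, then 176 (stated 176). These are not in dispute.

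**Why complete case repeats the primary model.** With a common baseline mean, the estimated effect is in essence (difference in 12-month means) − ρ × (difference in baseline means) among participants with both values. The pooled baseline mean cancels, so a baseline-only participant affects the result only through ρ and the covariate terms. Simulation agrees. With 500 participants and 20% missing, the two estimates correlated at 0.9997 or higher, and their mean absolute difference was 0.007–0.010 lb (SE about 1.2) and 0.011–0.014 PCS points (SE about 0.70). In a simplified model with informative missingness and a true effect of 7.7 lb, both gave 8.83 lb. The strength of that mechanism was assumed; the agreement is the point, not the amount of bias.

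**What a screen would see.** The plan defines none, so a logistic screen on arm, baseline outcome, their interaction and the strata was assumed. When poor responders in the intervention arm were more often missing, it fired in 5–6% of simulated trials, about its false-positive rate. When missingness depended only on baseline, where the primary model is valid, it fired in about 98%.

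**Effect on the estimate.** Overstatement = 0.2 × shift in the missing intervention participants.
- No benefit: 0.2 × 7.7 = 1.54 lb (true 6.16); 0.2 × 5.00 = 1.00 point (true 4.00).
- Half the benefit: 0.2 × 3.85 = 0.77 lb; 0.2 × 2.5 = 0.50 point.

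**Effect on significance.** SE = SD × √(1 − r²) × √(2/200). One-arm tipping shift = (effect − 2.2414 × SE) / 0.2. If the arms shift equally in opposite directions, divide by 0.4.

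| Scenario | SE | One arm | Opposite, each arm |
|---|---|---|---|
| Weight 7.7 lb | 1.216 | 24.9 | 12.4 |
| Weight 6.7 lb (conservative) | 1.802 | 13.3 | 6.7 |
| Weight 3.85 lb (assumed, half) | 1.216 | 5.6 | 2.8 |
| PCS 5.00 (t-test SE) | 0.888 | 15.05 | 7.5 |
| PCS 4.33 (t-test SE, conservative) | 1.025 | 10.2 | 5.1 |

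For PCS at 2.0 points the baseline-adjusted SE is needed, and the plan gives no correlation. It can be implied from E-LITE. Pooled change variance = (4.7² + 6.5²)/2 = 32.17, and r = (s₀² + s₁² − 32.17)/(2 s₀ s₁).
- SD 7.5 at both times: r = 0.71, SE 0.525, shift 4.1.
- SD 7.5 then 8.88: r = 0.77, SE 0.564, shift 3.7.
- SD 8.88 at both times: r = 0.80, SE 0.537, shift 4.0.

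So 3.7–4.1 points in one arm, or about 1.8–2.1 in each arm if they move in opposite directions. With assumed r of 0.5, 0.6 or 0.7 and SD 8.88, the one-arm shift is 1.38, 2.04 or 2.89.

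These figures hold the SE fixed. Delta-adjusted multiple imputation that recomputes it gives about 23 lb at 7.7 lb, about 17 points at 5.00 (r 0.77) and about 3.5 points at 2.0.

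**The case against.** The plan is not silent: it names pattern-mixture models, and complete case is offered only for mostly complete data, not as a test of MAR. A reader might infer that no analysis beyond MAR is planned at all. The text does not support that; the defect is the trigger.

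A reader might also infer that a modest shift would overturn the result. At the planned effects it takes about three times the effect. At E-LITE's 2.0 points, with correlations implied by E-LITE's own SDs, it takes about twice the effect, so missing intervention participants would have to fare worse than usual care. Using the unadjusted t-test SE from Section 5.6.1 at 2.0 points would give (2.0 − 1.99)/0.2 = 0.05 points, but that is not the planned baseline-adjusted analysis.

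Other data do carry information. For weight, Section 5.5.2 says "we will extract all outpatient-based weight measurements from CDW starting with 12 months prior index date through 27 months of follow up", and Table 5 lists outpatient and participant-measured weights as a secondary outcome. For SF-12, Section 2.3.1 reports that PCS gains correlated with weight loss, and SF-12 is collected again at 24 months. It would be wrong to say nothing informs a missing SF-12. None of these sources, however, is planned as a sensitivity analysis for a missing primary value.

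Retention letters, telephone follow-up and continued follow-up after stopping the intervention should reduce missingness. The 20% is a design allowance, and nothing in the documents shows missingness that differs by arm. Simulated bias or false-positive rates under informative missingness depend on assumed strengths and predict nothing for this trial.

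What stands is that the robustness shown above is never demonstrated under the plan unless the trigger happens to fire.

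**Conclusion.** The concern holds as a gap in sensitivity analysis, not as a flaw in the primary analysis. If nothing is detected, neither co-primary has a planned analysis that departs from MAR, and complete case cannot stand in for one.

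The main exposure is the effect size: up to about 1.5 lb or 1.0 PCS point if missing intervention participants had no benefit, and half that if they had half the benefit. This assumes 250 per arm, 20% missing, and usual-care non-responders behaving as MAR predicts.

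Significance is robust at the planned and conservative effects for a shift in one arm. At smaller effects it is less so, but the one-arm shift still exceeds the effect: 3.7–4.1 points against 2.0 at document-implied correlations, and 5.6 lb against an assumed 3.85 lb. It falls below the effect only with an assumed PCS correlation of about 0.5, or when the arms move in opposite directions (2.8 lb each against 3.85; about 1.8–2.1 points each against 2.0; 6.7 lb each, about equal to the effect, in the conservative weight scenario).

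Confidence is high on the wording and logic. The likely amount of bias is unknown.

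**What to change.** In Section 5.6.5, delete the detection condition and state that a delta-adjusted pattern-mixture analysis will always be run for both co-primary outcomes:
- Shift missing intervention-arm outcomes toward less benefit (heavier weight, lower PCS) relative to their MAR prediction.
- Vary the usual-care shift separately, including in the opposite direction.
- Report results at half and all of the assumed effect (3.85 and 7.7 lb; 2.5 and 5.00 points), then extend the shift until the conclusion changes and report that tipping point.
- Do not present agreement with complete case as support for MAR.

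Optionally, add a supportive analysis with auxiliary data: other CDW or participant-measured weights for weight, and CDW weights and the 24-month SF-12 for SF-12. State that it removes only part of any bias.

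The cost is a few lines of text and modest programming. Sample size, data collection, primary endpoint and primary model do not change. The downside is more results to report, with shifts that are judgements. Because the Abstract says 12-month questionnaires have been completed, date and record the change before outcomes are compared by arm.

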6.0 Reporting

6.1 *Safety Assessment*

Physical, psychological, social, legal or other risk will be low in association with participation in the proposed research. We base this assertion on the original diabetes prevention program where serious adverse event rates were similar in the intervention and placebo groups (NEJM, 2002;346:393-403). Moreover, [name] ELITE trial showed no study-related serious adverse events in the self-directed DVD group upon which the DELITE intervention is based.

To ensure unbiased determination across treatment arms, at each follow-up contact we will ask participants to complete a survey about potential adverse events (AE), serious adverse events (SAE) and unanticipated problems (UP) employing a body system-based assessment. A study investigator with appropriate clinical training and will assess (using participant self-report and chart review) each AE for duration (start and stop dates and times), expectedness in the study population, severity, outcome, treatment and relation to study activity.

The following are expected adverse events in the DELITE population of participants who have a high BMI, and adopt healthy eating and physical activity program:

- Gastrointestinal symptoms related to change in diet;
- Musculoskeletal symptoms or injury resulting from increased physical activity, including increasing symptoms such as chest discomfort, shortness of breath, and leg cramping;

- Development of weight associated disorders including diabetes, hypertension, liver disease, cardiovascular disease, asthma, COPD, clotting problems, and other lung related conditions;
- Development of other conditions associated with unhealthy health behaviors, such as from tobacco and alcohol disorders (e.g. cancer);
- Age related illnesses, such as pneumonia, urinary tract and skin infections.

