5.0 Study Procedures

5.1 Study Design

DELITE is a simple, two-arm PCT in which 500 Veterans with obesity will be randomized to usual care (UC) or UC plus the DELITE self-directed lifestyle intervention for 12 months. We will assess weight change from baseline via CDW over a 24-month period and self-report assessment at 12 and 24 months. We hypothesize that intervention participants will have more weight loss and greater improvements in self-reported physical function at 12 months relative to UC controls. The design is depicted in **Figure 5** and described below.

Figure 5. Overall study flow

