5.3.5.2 Intervention format, structure, and content.

Within two weeks of randomizing a participant to the intervention group, a DELITE lifestyle coach will call to confirm receipt of the intervention package, review the materials and instructions, confirm understanding, and address any questions.

The DELITE core curriculum consists of watching one ~25-minute GLB video session (see Table 2 for list of topics) each week for 12 weeks, and using a corresponding GLB handout. The GLB also includes additional “Physical Activity Resource” videos with a corresponding handout. Participants may watch the sessions on DVD or online through the University of Pittsburgh GLB training center. The lifestyle coach will instruct participants about how to use the MFP website or paper-tracking booklets, depending on preference, for self-monitoring which may include weight, food intake, physical activity, GLB materials used, and how to contact the lifestyle coaching via MFP secure messaging or phone if they have questions or would like guidance with the lifestyle program. A lifestyle coach will send standardized reminders through MFP secure messaging or via mail for participants who choose to use paper trackers. As recommended by guidelines, the main objective of the core curriculum is to facilitate gradual weight loss through successive and progressive changes in diet and physical activity and behavioral skills training.

Months 4-12 focus on continued self-directed/monitored gradual weight loss and maintenance, and use of additional GLB handouts. Participants will have access to a lifestyle coach via MFP secure messaging or telephone as desired for the 12 months of the intervention. The choice to engage with a lifestyle coach is strictly up to the participant and will occur as seldom or often as the participant chooses. Self-monitoring is key to success in behavioral weight-loss interventions.⁷¹ The lifestyle coach will continue to send standardized reminders throughout the 12 months of the interventions.

5.3.5.3 Intervention adherence.

Other than sending the standardized reminders (Section 5.3.5.2), DELITE will not use special strategies to maintain or improve participant adherence to the intervention.

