- Other weight loss interventions: We will monitor through CDW data extraction for participation in MOVE! and by patient report for participation in programs outside VA, and we will control for such use in secondary analysis.
- Engagement of participants to the intervention will be assessed by: Through MFP and/or mailed survey:
 - Number of GLB sessions viewed, modality used (DVD vs. online), and use of handouts;
 - Number and topic of contacts with lifestyle coaches.
- Cost: We will conduct a budget impact analysis and determine implementation costs using VA Managerial Cost Account (MCA) System.

Table 5. Measures and timing of data collection.

Variable	Potential source of data	12 months prior	3 months Baseline	12 months	24 months
Program reach, baseline characteristics, and covariates					
Height	CDW		x		
Comorbidities	CDW/self-report	x	x	x	x
Medications	CDW	x	x	x	x
Healthcare utilization	CDW	x	x	x	x
Distance from primary care clinic	CDW		x		
Demographics	CDW; Self-report		x		
Weight loss programs	CDW/self-report			x	x
Self-monitoring	Self-report			x	x
Outcome assessments					
Primary					
Weight	CDW (primary care-based measurement through 15 mos)		x		x
SF-12	Self-report		x	x	x
Secondary					
Weight	CDW (all outpatient measurements* through 27 mos) or participant measured*	x	x	*x	x
Physical activity	Self-report		x	x	x
Dietary quality/self-efficacy	Self-report		x	x	x
Sleep disturbance / impairment	Self-report		x	x	x
Blood pressure	CDW	x	x	x	x
HbA1c	CDW	x	x	x	x
Other weight loss interventions	CDW/self-report	x	x	x	x
Engagement	Self-report			x	x
Percent accepting invitation	Invitation response		x		
Cost**	MCA				x
Reach	CDW/self-report/study tracking		x		
Adverse Event Surveillance					
Event form	CDW/Self-report			x	x

**other potential sources are Health Economics Resource Center (HERC), Non-VA Medical Care Files, VA/CMS Data for Research, and VHA Support Services Center (VSSC) via the following tools: Compensation & Pension Record Interchange (CAPRI), the Computerized Patient Record System (CPRS), VistAWeb, VINCI.

5.5.3 Participant Payment:

After the 24-month time point, we will compensate participants \$20 for completing the 12- or 24-month survey packets. We will pay participants an additional \$10 if they complete both packets, for a total possible of \$30.

Following payment submission, we may mail a letter notifying participants that participation is complete and payment has been submitted.

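### Adverse-event collection is scheduled only at months 12 and 24, so during a participant's 12-month intervention the safety reports and the cessation rule rest on unscheduled information, one source of which exists in one arm only

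*Combined protocol and SAP*

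**What the plan says.** Section 6.1 states that "at each follow-up contact we will ask participants to complete a survey about potential adverse events (AE"), serious events and unanticipated problems, and gives even-handed ascertainment between arms as the reason. It does not define the contacts or give months. Each event is to be assessed, from self-report and chart review, for items that include its start and stop times.

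Table 5 has one row under "Adverse Event Surveillance": an event form, sourced from CDW or self-report, marked at 12 and 24 months. Section 5.1 agrees, with "self-report assessment at 12 and 24 months", and describes the active arm as "UC plus the DELITE self-directed lifestyle intervention for 12 months".

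Two processes use adverse-event information while participants are exposed:

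- Section 5.7: on pregnancy, on the team learning of a serious physical or mental health problem, or on a primary care provider's notice, "the participant will cease participation in the intervention activities of the research".
- Section 5.6.6: "We will provide interim safety reports semi-annually to the Data Monitoring Committee (DMC"). Section 6.3 adds that these reports cover every event, by unlabelled arm, that unexpected related serious events are reported when discovered, and that the DMC may consider early termination for safety.

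**The concern.** The data schedule and the processes that use the data do not match. The reporting cycle is six months, but the first scheduled question to a participant comes at twelve, when there is no intervention left to cease. Until then, whatever reaches the study team does so unprompted, and one of the routes, the lifestyle coach, is open to the intervention arm alone.

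Two things are at stake. The DMC could be reviewing early harm without scheduled data on the people currently exposed. And if coach-volunteered events enter the counts for each arm, the between-arm comparison mixes a source common to both arms with one that is not, contrary to the stated purpose of Section 6.1.

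**Working it through.** The plan gives no figure to reproduce; this is a comparison of schedules.

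**Step 1. Contacts after randomization and before month 12.**

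| Contact | Arm | Stated content | Asks about harm? |
|---|---|---|---|
| First coach call, within two weeks (5.3.5.2) | Intervention | "a DELITE lifestyle coach will call to confirm receipt of the intervention package", go through materials, answer questions | Not described |
| Standardized reminders (5.3.5.2) | Intervention | Prompts about the program | Not described |
| Later coach contact (5.3.5.2) | Intervention | At the participant's choice | Unscheduled |
| Letters (5.5) | Both | "we will send a letter reminding them of their participation in the study at around the 4th, 8th, 16th, and 20th month after randomization" | Not described |
| Event form (Table 5) | Both | Adverse events | First at month 12 |

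Scheduled adverse-event collections before month 12: 0. The first falls at month 12 and the second at month 24, which is 24 − 12 = 12 months after the intervention ends. No window is given for the 12-month survey, so its exact position relative to the end of the intervention is not fixed.

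**Step 2. Delay for one participant.** The core video phase is 12 weeks, or 12 / 4.345 = 2.8 months. An event in that phase is first asked about between 12 − 2.8 = 9.2 and 12 months after onset. The next semi-annual report can add up to 6 months. For an event at month 1, the delay is 12 − 1 = 11 months to the form and up to 11 + 6 = 17 months to a DMC meeting.

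**Step 3. The trial as a whole.** The accrual period is not stated. I assume uniform entry of 500 participants over A months, with reports counted from the first randomization. No form is due by the month-6 report, and the first falls due at month 12. The share of all planned exposure already elapsed at month 12 is (12 − A/2)/12 when A ≤ 12 and 6/A when A > 12. By month 18, forms are due from 500 × min(1, 6/A) participants, out of 500 × min(1, 18/A) randomized.

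| A (assumed, months) | Exposure elapsed when first form is due | Forms due by month 18 | Randomized by month 18 |
|---|---|---|---|
| 6 | 75% | 500 | 500 |
| 12 | 50% | 250 | 500 |
| 18 | 33% | 167 | 500 |
| 24 | 25% | 125 | 375 |
| 30 | 20% | 100 | 300 |

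So reports after the first year are not empty. What they lack is scheduled data on participants still within their 12 months: for example 500 − 250 = 250 people at month 18 if A = 12.

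**Step 4. Symmetry between arms.** Provider notice, discovery of serious events and chart or CDW awareness can arise in either arm. Coach contact cannot. Section 6.3 asks for all events and does not separate them by source, so the two kinds can be pooled in one count.

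**The case against.** Several points on the other side stand.

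- A reader might infer that the DMC sees only spontaneous reports for months 0 to 12. That is not so. The 12-month survey covers those months in both arms, and with staggered entry its results reach the DMC while later participants are still exposed.
- A reader might infer that Section 5.7 promises screening that never happens. Its health-problem and provider triggers are reactive: they act when the team learns of something. Only the pregnancy trigger is not worded that way.
- A reader might infer that interim counts are tilted toward the coached arm by some amount. The documents give no event or volunteering rates and do not say that coach-volunteered events enter the comparison, so the direction is plausible but no size can be given.
- Table 5 marks need not be extraction dates. Blood pressure is marked at fixed points although Section 5.5.2 extracts it over a continuous span. CDW event data may likewise cover the whole period, but nothing says they are drawn or reviewed before month 12.
- The protocol calls the risk low and reports no study-related serious events in the predecessor's self-directed arm. That supports light surveillance. It does not make the sources equal between arms.
- The Abstract reports the 12-month questionnaires as completed and the 24-month ones as under way, so new prompts during exposure would come too late for this cohort.

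Reading the contacts in Section 6.1 to include the month-4 and month-8 letters would close the gap, but neither Table 5 nor the description of those letters supports that reading.

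**Conclusion.** The point holds per participant and for scheduled collection. Between randomization and month 12 there is no scheduled adverse-event question in either arm. Section 5.7 and the semi-annual reports then draw, for anyone still exposed, only on unscheduled sources, and one of these exists in the intervention arm alone. The delay to the first scheduled question is about 9 to 12 months for events in the core phase, with up to 6 more to a DMC report. The trial-level shares depend on the assumed accrual period.

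The documents do not show that participants went unmonitored, that reports were empty throughout, or that any between-arm difference was produced. They leave open what fed these processes, and they allow a safety table that combines events ascertained differently in the two arms. That second part can still be corrected.

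**What to change.** 1. Reconcile Section 6.1 with Table 5, Section 5.7 and Section 6.3: list the contacts at which the adverse-event survey is given, and state what feeds the cessation rule and the DMC reports in months 0 to 12. The rule in Section 5.7 is left as it is.
2. Run the CDW event extraction identically in both arms, timed to the semi-annual DMC reports for the remaining follow-up, and retrospectively by onset date for months 0 to 12. CDW is already a listed source for the event form. It also reaches most people who did not return a survey, except those who declined CDW follow-up on withdrawal.
3. Base between-arm adverse-event comparisons only on CDW and scheduled-survey events, and list coach-volunteered events separately.

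The cost is a protocol clarification, a repeated query taking a few analyst hours per DMC cycle, and more events to classify. Care outside the VA may be missed by CDW, which should be stated with the tables.
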